8.8.2 Clinical laboratory tests

Clinical laboratory tests include haematology, clinical chemistry, and urinalysis panels. The complete list of clinical laboratory parameters is presented in Table 3 below.

Table 3 Clinical laboratory tests

Haematology	Clinical Chemistry	Urinalysis
Basophils (absolute)	Alanine Aminotransferase (ALT)	Blood Cells (Erythrocytes, Leukocytes)
Basophils/Leukocytes	Albumin	Glucose
Eosinophils (absolute)	Alkaline Phosphatase	Ketones
Eosinophils/Leukocytes	Aspartate Aminotransferase (AST)	Microscopic evaluation (i.e. Bacteria, Squamous Epithelial Cells, Mucous Fiberis, Urine, Crystals)
Haematocrit	Bilirubin (Total)	Protein
Haemoglobin	Calcium	
Lymphocytes (absolute)	Chloride	
Lymphocytes/Leukocytes	Creatinine	
Monocytes (absolute)	Glucose	
Monocytes/Leukocytes	Lactate dehydrogenase (LDH)	
Neutrophils (absolute)	Potassium	
Neutrophils/Leukocytes	Protein (Total)	
Platelet Count	Sodium	
Red Blood Cell (RBC) count	Urea (BUN)	
White Blood Cell (WBC) count		
Anti-tissue transglutaminase (tTG) IgA and IgG		
Anti-tTG6 IgA and IgG		

Clinical laboratory parameters will be obtained at times indicated in the study schedule ([Appendix 1](#)). Blood and urine samples collected at the Screening Visit will require a minimum 8-hour fast.

All clinically significant findings during the study should be followed until resolution or until the finding is clinically stable. Subjects may be withdrawn from study drug if the Investigator or Sponsor deems the clinically significant finding compromising to the subject's safety; however, these subjects will continue to be followed-up per protocol, unless consent is withdrawn.

Detailed information regarding the collection and handling of clinical laboratory specimens, including blood draw totals for each visit and instructions for re-testing of missing or

compromised specimens, can be found in a separate Central Laboratory Manual or equivalent document supplied by the central clinical laboratory.

Laboratory test values, including anti-tTG and anti-tTG6 antibodies, will be presented by individual listings with flagging of values outside the normal ranges (normal ranges will be presented in statistical analysis report appendix). Absolute laboratory values and changes from baseline will be presented using summary statistics by treatment group and visit. Clinical laboratory variables will also be explored in mean curves. Urinalysis parameters will not be included in figures. ITT analysis population will be used.

Anti-tTG6 antibody data will be analysed internally by Celimmune.

Additionally, shift table of liver function tests (Aspartate Aminotransferase (AST), Alanine Aminotransferase (ALT), Bilirubin (Total) and Alkaline Phosphatase (ALP)) will be created. Count and frequencies by treatment group will be presented in the shift table.

8.8.3 Physical examination

Physical examination will be performed at times indicated in the study schedule ([Appendix 1](#)) and includes an examination of general appearance; head, eyes, ears, nose, throat (HEENT); lymph nodes; respiratory; cardiovascular; gastrointestinal; musculoskeletal; neurological, psychological and dermatological systems.

Physical examination results will be tabulated by treatment group, visit, body system, result (normal, abnormal, not done) and clinical significance (yes, no) and listed using ITT analysis population.

8.8.4 Vital signs

Vital signs include body temperature, pulse rate, systolic blood pressure (sitting), diastolic blood pressure (sitting), and respiratory rate. BMI and BSA will be obtained from measurements of body weight and height. Vital signs will be measured at screening and all other study visits.

Vital signs will be listed and changes from baseline and absolute values will be presented using summary statistics by treatment group and visit. Mean absolute values and change from baseline values in weight will also be presented graphically by time point and treatment group.

ITT analysis population will be used for the analysis of vital signs

8.8.5 Immunogenicity

Immunogenicity, i.e. the generation of anti-drug antibodies (ADA), is a potential risk for any biologic therapeutic. Immunogenicity may lead to injection reactions and to loss of efficacy when the antibodies are neutralizing and high-titer.

A two-tiered immunogenicity testing approach will be used in order to determine if a sample contains ADAs. Samples will be initially tested in an immunoassay. Samples that test positive for binding antibodies will then be tested in an assay to detect neutralizing antibodies (NAb). Immunogenicity testing will be performed at times specified in schedule of study procedures ([Appendix 1](#)).

Immunogenicity will be tabulated by treatment group, visit, ADA test result (negative, positive) and neutralizing antibodies test result (negative, positive) and listed. ITT analysis population will be used.

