1.6 EFFECTS OF AMG 714 IN HUMANS

The original hybridoma-derived material produced by Genmab (AMG 714-HYB) was evaluated in subjects with RA in a Phase 1 study (Hx-IL15-001) and a Phase 2 study (20030210). [REDACTED] AMG 714 is now produced by a CHO cell line. [REDACTED]

[REDACTED] AMG 714-CHO was studied in a first-in-human trial to investigate safety, tolerability, pharmacokinetics, and pharmacodynamics in healthy subjects (Phase 1 Study 20050193) and in a proof-of-concept study in patients with psoriasis (Phase 2 Study 20060349). To date, AMG 714 has been shown to have clinical effect in RA; tolerability comparable to placebo in ~200 subjects exposed (including ~140 exposed for 12 weeks of bi-weekly dosing); a favorable pharmacokinetic profile with 3 weeks half-life; and no significant immunogenicity signal.

All completed clinical studies of AMG 714-CHO and AMG 714-HYB are summarized in Table 3.

Table 3. Summary of AMG 714 Clinical Studies

Study Number (Phase)	Key Design Features	Dose Route, Duration	Study Population	Status
AMG 714-CHO				
20050193 (Phase 1; Amgen)	Double-blind, placebo-controlled, single SC or IV doses, dose-escalation study	SC doses: 0, 30, 100, 300 or 700 mg (cohorts 1 to 4) IV dose: 0 or 100mg IV infusion (cohort 5) ^d Single dose	40 healthy subjects	Completed
20060349 (Phase 1b/2a; Amgen)	Double-blind, placebo-controlled, multiple SC doses, dose-escalating study	0 or 150 mg SC (cohort 1) 0 or 300 mg SC (cohort 2) Dose every 2 weeks for 12 weeks	22 subjects with moderate to severe psoriasis	Completed ^b
AMG 714-HYB				
Hx-IL15-001 (Phase 1; Genmab)	Double-blind, placebo-controlled, single SC infusion, dose escalation, study with open-label, repeat-dose (4 weekly doses) follow-up	Initial single dose: 0 or 0.15 to 8 mg/kg SC infusion Repeated dose: 0.5 to 4 mg/kg SC infusion once weekly for 4 weeks 5 doses total over 8 weeks	30 subjects with RA ^c	Completed
20030210 ^d (Phase 2; Genmab/Amgen)	Double-blind, placebo-controlled, multiple SC infusion, parallel-group, multicenter study	0 or 40 to 280 mg SC infusion dose every 2 weeks for 12 weeks with initial 200% loading dose	180 subjects with RA	Completed

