11.2.5 Visit 3 (Week 2/Day 14)

- Document visit in the EDC system.
- Collect vital signs.
- Measure body weight.
- Perform physical examination to include an examination of general appearance; HEENT; lymph nodes; respiratory; cardiovascular; gastrointestinal; musculoskeletal; neurological, psychological and dermatological systems.

- Complete PGA BEFORE study drug administration.
- Allow the subject to complete the Patient Global Assessment of Disease (PtGA) BEFORE study drug administration.
- Collect blood and urine for clinical laboratory testing.
- Collect blood sample for PK, ADA and biomarkers BEFORE start of study drug administration. Record date and actual time of sampling.
- Collect stool for iVYLISA GIP test. The stool sample will be produced within 3 days prior to, or after, the scheduled study visit.
- Perform urine pregnancy test on FOCBP.
- Administer study medication. See section 18 for administration procedures.

NOTE: Subject should remain in the clinic for a minimum of 1 hour after the end of study drug administration to monitor for new adverse events.

- Assess AEs.
- Monitor for changes to concomitant medications.
- Remind subjects to complete the BSFS at each occurrence of a bowel movement and the CeD PRO daily.
- Remind subject to complete the weekly GSRS.
- Provide subject with iVYLISA GIP test kit and instructions for home collection.

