11.2.10 Visit 8 (Week 12/Day 84)

NOTE: DO NOT ADMINISTER STUDY MEDICATION AT THIS VISIT

- Document visit in the EDC system.
- Allow subject to complete SF-12 v. 2 and EQ-5D.
- Collect vital signs.
- Measure body weight.
- Perform physical examination to include an examination of general appearance; HEENT; lymph nodes; respiratory; cardiovascular; gastrointestinal; musculoskeletal; neurological, psychological and dermatological systems.
- Complete PGA BEFORE study drug administration.
- Allow the subject to complete the Patient Global Assessment of Disease (PtGA), BEFORE study drug administration.
- Collect blood and urine for clinical laboratory testing.
- Collect blood sample for PK, ADA and biomarkers. Record date and actual time of sampling.
- Collect Whole Blood for Flow Cytometry.
- Perform serum pregnancy test on FOCBP.
- Collect stool for iVYLISA GIP testing. The stool sample will be produced within 3 days prior to, or after, the scheduled visit.
- Assess AEs.
- Monitor for changes to concomitant medications.
- Dietitian assessment of the GFD. This assessment can be conducted by phone, provided it is conducted within the allotted visit window.
- Remind subjects to complete the BSFS at each occurrence of a bowel movement and the CeD PRO daily.
- Remind subject to complete the weekly GSRS.
- Provide subject with iVYLISA GIP test kit and instructions for home collection.
- Perform endoscopy and collect biopsy specimens within 7 days of Visit 8.

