14.6. IMMUNOGENICITY

A two tiered immunogenicity testing approach will be used in order to determine if a sample contains ADAs. Samples will be initially tested in an immunoassay (ELISA). Samples that test positive for binding antibodies will then be tested in a bioassay (CTLL-2 cell line that responds to recombinant human IL-15), to detect neutralizing antibodies (NAb).

The sensitivity of the ELISA assay is approximately 20 ng/mL and the lower limit of reliable detection (LLRD), even in the presence of serum levels of drug, is approximately 250 ng/mL. The LLRD of the bioassay is approximately 1.5 µg/mL.

In addition to these existing validated methods, the sponsor will develop and validate a bridging immunoassay (for binding ADA) and a target binding method (for neutralizing ADA) in the Meso Scale Discovery (MSD) platform to potentially improve performance. The final method chosen will be described in the study manual and regulatory submissions

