18.3 DOSE RATIONALE

The selection of dosing level for the CELIM-RCD-002 study is based on a desire to strike the appropriate benefit/risk balance, striving for efficacy by testing an adequately high dose of AMG 714 in an attempt to quickly alleviate the presumed effects of IL-15 on aberrant IELs and on RCD-II symptoms while using a dose that is similar to doses used in prior studies with tolerability comparable to placebo. The highest clinical dose of AMG 714 used chronically IV has been 8 mg/kg IV single dose followed by 4 mg/kg IV q2w for 8 weeks. The proposed dose of 8 mg/kg IV for 10 weeks, q2w with an extra dose at week 1, is modestly higher in order to account for the presumed protein-losing enteropathy typical of RCD-II (up to 40% protein loss can be expected based on albumin levels in RCD-II patients) and for the larger target organ area (small bowel as compared to more localized joints).

While exposure data at relevant IV doses are only available in healthy volunteers, the high bioavailability of 86.6% observed in healthy volunteers and the expected protein-losing enteropathy in RCD-II suggest that it is unlikely RCD-II patients will present with meaningfully higher exposures than those studied in healthy volunteers.

Human studies to date, as well as modeling, support the dosing regimen of an IV infusion of 8 mg/kg AMG 714 a total of 7 times over 10 weeks, over 120 minutes. The highest doses of AMG 714 studied in clinical trials are a single SC dose of 700 mg, SC doses of 300 mg every two weeks for 12 weeks, and the aforementioned 8 mg/kg IV single dose followed by 4 mg/kg q2w for 8 weeks, all regimens with no safety signals identified to date. In addition, the proposed study regimen has adequate safety margins based on toxicology. [REDACTED]

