The expected ranges provided by the dosing regimen are not only presumed to be tolerable, but also expected to be efficacious based on available mechanistic data. While there is no clinical experience with AMG 714 in RCD-II nor any understanding of the potential PK/PD relationships in this disease, incubation of duodenal biopsies from RCD-II patients with 10 µg/mL of AMG 714 for 48 hours effectively inhibited endogenous activation of JAK3 and STAT5 (Malamut *et al*, 2010). Serum concentrations in this study are predicted to always exceed 59 µg/mL, and following a dose at 1 week to exceed 96 µg/mL, even after accounting for possible leakage of protein in the intestine. Even if local mucosal tissue levels were lower

than serum levels, these serum values are several times higher than the 10 µg/mL concentrations that were effective in the *ex-vivo* setting, and provide a reasonable expectation that the tissue levels achieved will be efficacious.

Serum exposure will be monitored with frequent PK sampling and with an unblinded interim analysis to be conducted by the DSMB, when the tenth patient reaches Week 4. Tissue effects will be monitored with experimental biomarkers to be measured in the biopsies to be obtained in the study.

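### SAP 8.8.5 has no category for a negative antibody result obtained at a drug level that may mask antibody, so uninterpretable active-arm results can be tabulated as negative

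*SAP*

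**What the plan says.** **Sampling.** Protocol Table 1 draws serum for anti-drug antibodies (ADA) at Visit 1 and then at Weeks 2, 4, 8, 12 and 16. A PK sample is scheduled at every one of those visits. At Visit 3 the instruction is "Collect blood sample for PK, ADA and biomarkers BEFORE start of study drug administration". At Visit 8, when no drug is given, it is "Collect blood sample for PK, ADA and biomarkers. Record date and actual time of sampling".

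**Assays.** Protocol 14.6 describes two tiers. The first is a binding ELISA with a limit of reliable detection of about 250 ng/mL. The protocol says this limit holds with drug in the serum, but not at what drug level. The second tier follows: "Samples that test positive for binding antibodies will then be tested in a bioassay (CTLL-2 cell line that responds to recombinant human IL-15". Its limit is about 1.5 µg/mL, and nothing is said about drug tolerance. The same section plans a bridging immunoassay and a target-binding neutralising method, and leaves the final choice to the study manual and regulatory submissions. SAP 8.8.5 keeps the two tiers but names no assay.

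**Reporting.** SAP 8.8.5: "Immunogenicity will be tabulated by treatment group, visit, ADA test result (negative, positive) and neutralizing antibodies test result (negative, positive) and listed". Protocol 22.8.2 asks for the number and percent of subjects who develop each type of antibody.

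**Exposure.** Protocol 18.3: "Serum concentrations in this study are predicted to always exceed 59 µg/mL, and following a dose at 1 week to exceed 96 µg/mL", after allowing for intestinal protein loss. Protocol 1.6 describes "a favorable pharmacokinetic profile with 3 weeks half-life".

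**The concern.** AMG 714 acts by inhibiting IL-15 (Protocol 1.4). The bioassay in Protocol 14.6 reads the response of cells to IL-15. A neutralising antibody would reveal itself by undoing the drug's block on that response, and drug already present in the serum sample maintains the block. In the binding tier, circulating drug can compete for the same antibody. In either tier, a negative obtained at a high drug level may mean that there is no antibody, or that the assay could not see it. A two-way table cannot separate the two.

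Any such masking would occur only in the AMG 714 arm and only toward fewer positives. Immunogenicity is a named safety endpoint (Protocol 5.4, SAP 2). SAP 8.8.5 itself says that high-titre neutralising antibodies can cause loss of efficacy, so a false negative could also mislead the reading of a non-responder. Protocol 2.2 extends monitoring beyond the study only for ADA that has tested positive.

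**Working it through.** **1. The plan's own figures.** The inputs behind 59 and 96 µg/mL are redacted (Protocol Appendix G), so they cannot be rebuilt from source. They can be checked against each other. Take one compartment with equal doses on Days 0, 7, 14, 28, 42, 56 and 70, and half-life h:

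C(t) = C0 × Σ 2^(−(t − d)/h), summed over doses d before t, with C0 = 59 × 2^(7/h) so that C(7) = 59.

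At h = 16 days, C0 = 59 × 1.354 = 79.9. The Day 84 sum is 1.203, so C(84) = 96.1, the lowest trough after Day 7. The two figures therefore agree with each other at a half-life of about 16 days. That is close to 21/1.4 = 15 days, which is what a 40% rise in clearance would give.

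**2. Weeks 2, 4, 8 and 12.** The first three samples are pre-dose, after the Week 1 dose. Week 12 is 14 days after the Day 70 dose, one full dosing interval. All four are troughs to which the prediction of more than 96 µg/mL applies.

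**3. Week 16.** This visit is 42 days after the last dose: 42/21 = 2 half-lives. Carrying 96 µg/mL forward from Day 84 gives C = 96 × 2^(−28/h), or 96 × 2^(−35/h) if the visit falls 7 days late:

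| Half-life h | Day 112 | Day 119 |
|---|---|---|
| 21 days (Protocol 1.6) | 38.1 µg/mL | 30.2 µg/mL |
| 16 days (step 1) | 28.5 µg/mL | 21.1 µg/mL |
| 12.6 days (21 × 0.6) | 20.6 µg/mL | 14.0 µg/mL |

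The 12.6-day value is an assumption. It shortens the half-life by 40%, prompted by Protocol 18.3: "up to 40% protein loss can be expected based on albumin levels in RCD-II patients". Using the step 1 model's own Day 84 value in place of 96 widens the Day 112 range to 16.1 (h = 12.6) to 49.4 µg/mL (h = 21). The order of magnitude does not change.

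**4. Samples affected.** If all 16 AMG 714 subjects are fully dosed, 16 × 5 = 80 post-dose samples are scheduled. Of these, 16 × 4 = 64 are at a predicted level above 96 µg/mL.

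**5. Samples not affected.** The 8 placebo subjects carry no drug, and neither do Visit 1 pre-dose samples. A subject who stops after one to three doses but stays on the visit schedule (Protocol 20.2.1) would have about 0.5 to 7 µg/mL at Week 16, under the step 1 model with h = 15 to 21 days.

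**6. Choice of denominator.** Suppose every fully dosed sample exceeded assay tolerance and one of the 16 subjects tested positive at a visit. If inconclusive results are dropped, the rate is 1/1 = 100%. Over all subjects tested it is 1/16 = 6%, with 15/16 = 94% inconclusive. Only the second describes the data honestly.

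**The case against.** The strongest objection is that binding status is decided in the first tier alone. Only binding-positive samples reach the neutralising assay, so a blocked bioassay cannot turn any subject ADA-negative. It can only mislabel the neutralising column for subjects already reported as ADA-positive. For the first tier the protocol asserts detection at about 250 ng/mL with drug present, and Protocol 2.2 promises validated methods. The bioassay may not even be the assay used. All of this stands. A reader might infer that the table is bound to count masked samples as antibody-negative; the documents do not support that.

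A reader might also divide drug level by assay limit (96/1.5 = 64, for example) and take the ratio as the degree of masking. It is not: one figure is a drug concentration and the other an antibody concentration, and sample preparation is not described. Likewise, the 10 µg/mL in Protocol 18.3 comes from biopsy incubation and is not an assay tolerance.

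Two mitigating facts are fair. ADA results and drug concentrations are both listed (SAP 8.8.5 and 8.7.5), so a reader could cross-check them by hand. The endpoint is also descriptive, in a proof-of-concept trial of 24 subjects. Neither supplies a rule for a negative obtained above tolerance.

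The one earlier positive for binding and neutralising antibody (Protocol 1.8.2.1) shows that detection is possible. It came at Day 57 after a single 100 mg IV dose, so it does not show tolerance at the concentrations predicted here.

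**Conclusion.** The point holds as a gap in the reporting rule. In fully dosed AMG 714 subjects every scheduled post-dose ADA sample is drawn with drug predicted at tens of µg/mL, and SAP 8.8.5 offers only negative or positive with no reference to that level. A masked sample can therefore be reported as negative. The risk is clearest for neutralising results of binding-positive samples if the CTLL-2 bioassay is used. In the binding tier it is possible but unproven, because the drug level behind the 250 ng/mL limit is not given and the final assays were left open.

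It would go too far to say that all antibody samples are compromised, or that the active-arm rate is known to be biased toward zero. Placebo subjects and early stoppers carry little or no drug, and the tolerance of the final methods is not in the documents.

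The conclusion rests on the protocol's predicted lower bounds and, for Week 16 only, on one-compartment decay with a half-life of 12.6 to 21 days. No hypothesis test or go/no-go rule is affected. The change should be made because the endpoint is a named safety endpoint and the correction is cheap.

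**What to change.** In SAP 8.8.5:

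- Name the final binding and neutralising assays and state the validated drug tolerance of each.
- Classify each result in each tier as positive, negative or inconclusive. Inconclusive means a negative result with paired serum AMG 714 above that assay's tolerance.
- Report the number and percent of subjects in each of the three categories out of all subjects tested in that tier, by arm and visit. Do not report a rate over evaluable samples only: removing negatives but not positives would inflate it. This keeps the subject as the unit, as Protocol 22.8.2 requires.
- State that neutralising status is undetermined where the binding result is inconclusive.

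The cost is SAP wording and one merge of the PK and ADA datasets. PK is already drawn at every ADA visit, so no sample or visit is added. The downside is that fewer results can be called negative, and the immunogenicity statement may be less favourable. If the final assays tolerate these drug levels, the inconclusive column will be empty and the negative statement will be better supported.

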8.8.6 Other safety variables

8.8.6.1 Pregnancy test

All females of child bearing potential (FOCBP) will have urine or serum pregnancy tests throughout the study as outlined in schedule of study procedures ([Appendix 1](#)). Subjects who become pregnant during the study will be withdrawn from participation and the outcome of the pregnancy followed.

Pregnancy test results will be listed by treatment group, visit, test type (serum, urine) and result (negative, positive). ITT analysis population will be used for presenting pregnancy test results.

8.8.6.2 Prior and concomitant medications

Prior and concomitant medications will be collected throughout the study and coded using the World Health Organization Drug Dictionary (WHO DD) 2014 September version.

Prior and concomitant medication will be listed for ITT analysis population.

